12. SAFETY ANALYSES

All safety analyses will be performed for the Safety population as defined in Section 6.4. These data will not undergo any inferential statistical analysis. All safety analyses described below will be performed on data collected through the Week 60 study visit for the primary safety. The safety data from individualized follow-up period will be listed for any data available.

Section 9.2.1 details the algorithm for deriving baseline values. In the event that a baseline value for an assessment cannot be derived for a subject, the subject will be excluded from the change from Baseline analysis for that assessment; however, the subject's data will still be included in visit assessment summaries and analyses.

12.1. Extent of Exposure

Each subject is expected to receive 17 injections of study drug over the 56-week treatment period (two injections for a total of 40 mg at Weeks 0 and 4; 1 injection of 20 mg at all remaining treatment period study visits). Descriptive statistics will be used to summarize a subject's exposure (i.e. the number of injections each subject received) for each treatment group.

Percentage subject compliance will be defined as the number of injections received/17 planned injections. Percentage compliance will be summarized using descriptive statistics for each treatment group. The number and percentage of subjects receiving 100%, $\geq 80\%$ - $<100\%$, $\geq 60\%$ - $<80\%$, $\geq 40\%$ - $<60\%$, $\geq 20\%$ - $<40\%$ and $<20\%$.

Each subject's treatment exposure and compliance will be presented in a data listing.

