3.1. Study Design

This is a global, multicenter, randomized, double-blind, placebo-controlled, parallel-group study to assess the efficacy, safety, and tolerability of ofatumumab SC in subjects with PV, who have failed a previous attempt to taper steroid dosing (ie, had a disease flare during the taper attempt). The study includes a Screening Period, a Core Study Period (consisting of the 56-week Treatment Period and 4-week Follow-up visit), and an Individualized Follow-up Period (as applicable).

Subjects will visit the clinic during Screening; at Baseline (Week 0); at Weeks 2, 4, 6, and 8; and then every 4 weeks from Week 8 through Week 60. Subjects will also have

structured phone visits between each of the clinic visits from Week 10 through Week 22 (see [Appendix 14](#)). It is anticipated that total duration of participation in the Core Study Period will be approximately 72 weeks.

A Screening Period of 2 to 12 weeks will occur prior to randomization to allow subjects to achieve disease control (no new lesions for ≥ 2 weeks) [[Murrell, 2008](#)] using a stable oral dose of prednisone/prednisolone (20 mg/day up to 120 mg/day or 1.5 mg/kg/day [whichever is higher] for ≥ 2 weeks). Multiple visits to the clinic are permitted during this Screening Period to assess disease status and to adjust the oral prednisone/prednisolone dose. Once disease control is achieved, subjects who continue to satisfy the eligibility criteria may be randomized. All screening procedures should be completed within 12 weeks of informed consent being given.

At the Baseline Visit (Day 0), approximately 136 eligible subjects will be centrally randomized 1:1 across 2 strata (disease duration [≤ 1 year, >1 year] and baseline prednisone dose [<60 mg/day, ≥ 60 mg/day]) to receive SC administration of ofatumumab 20 mg or placebo once every 4 weeks (with an additional 20-mg 'loading' dose at both Week 0 and Week 4) for a total of 56 weeks (total of 17 injections across 15 monthly dosing visits).

[figure not shown]
Two weeks after the first dose of ofatumumab SC or placebo (ie, Week 2), the oral steroid dose will be gradually reduced according to a fixed dose-taper schedule with a goal of reducing (ie, to ≤ 10 mg/day) or eliminating the dose of prednisone/prednisolone (see [Table 3-2](#)).

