4.4.2. Discontinuation of Investigational Product

Subjects must discontinue investigational product for any of the following reasons:

- Sponsor request, for reasons such as significant protocol deviation (and after discussion with the investigator).
- Study is terminated by the Sponsor.
- Subject meets PML discontinuation criteria (see [Appendix 4](#)).
- Subject develops any other serious opportunistic or atypical infection.
- Subject meets liver chemistry stopping criteria (see [Appendix 3](#)).
- Subject initiates treatment with a prohibited PV disease-modifying drug.
- Subject becomes pregnant.
- Subject experiences a serious or life-threatening cardiac arrhythmia.

Any subject who discontinues from the Treatment Period should complete an Early Withdrawal Visit and transition into the Individualized Follow-up Period for important safety monitoring (as applicable; see Section 3.1.3), unless he/she meets a criterion for mandatory withdrawal from the study (see Section 4.4.3).

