4.2. Final Analysis

The study was terminated early and the final analysis will be conducted on the available data.

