10.2. Protocol Deviations

Subjects who fail to fulfill any of the inclusion/exclusion criteria will be tabulated for each treatment group and listed for each subject in the ITT population.

Protocol deviations will be tracked by the clinical team on an on-going basis through the completion the individualized follow-up period (or early withdrawal from the study) for all subjects and will be listed by subject. The number and percentage of subjects with any protocol deviation and the number and percentage of subjects experiencing each protocol deviation category will be summarized for the ITT population.

Specific criteria for what constitutes a major protocol deviation (i.e. causing exclusion from the Per Protocol population) will be identified by the study team prior to study unblinding. The following criteria may be considered:

- Not meeting key inclusion/exclusion criteria
- Withdrawal criteria met but subject not withdrawn
- Taking prohibited concomitant medications
- Not being compliant with the study medication dosing schedule

Please refer to Section 6.3 for a discussion of protocol deviations as they pertain to the PP population.

The analysis sets and severity codes used in the trial programming are listed in below Table, which includes the analysis set codes 1-5 and the severity codes 0, 1, 5, 8 and 49 for the double-blind treatment period.

Table 10-1 The analysis populations and severity codes

Analysis set codes	Deviation Severity Codes		
1 = Screening Population 2 = Intent-to treat Population 3 = Per protocol Population 4 = Safety Population	0 = Exclude patient from all efficacy analyses 1 = Exclude patient from per-protocol analysis 8 = Exclude patient from all analyses		
	Deviation Severity Codes		
Analysis set (code)	0	1	8
Screening Population (1)	Yes	Yes	No
Intent-to-Treat population (2)	No	Yes	No
Per Protocol Population (3)	No	No	No
Safety Population (4)	Yes	Yes	No

Note: 'Yes' means include in the analysis population, 'No' means exclude from the analysis population.

The number and percentage of subjects with any major protocol deviation and the number and percentage of subjects experiencing each major protocol deviation category will be summarized for the ITT population. Major protocol deviations with deviation category and severity codes will be identified in the protocol deviations listing presented by subject for the ITT population.

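### Compliance is computed against all 17 planned injections in a terminated study, so subjects given every dose due but stopped before Week 56 are reported below 100%

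*SAP*

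**What the plan says.** SAP section 12.1 starts from the full course: "Each subject is expected to receive 17 injections of study drug over the 56-week treatment period", made up of "two injections for a total of 40 mg at Weeks 0 and 4; 1 injection of 20 mg at all remaining treatment period study visits". Protocol section 3.1 gives the same total: "total of 17 injections across 15 monthly dosing visits". SAP section 12.1 then sets the measure: "Percentage subject compliance will be defined as the number of injections received/17 planned injections". The percentage is summarised by arm and split into six bands, from 100% down to below 20%. The number of injections received is summarised separately as exposure, and both are listed by subject.

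On termination, SAP section 4.2 says: "The study was terminated early and the final analysis will be conducted on the available data". Protocol section 4.4.2 opens its list with "Subjects must discontinue investigational product for any of the following reasons", and one entry is "Study is terminated by the Sponsor".

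SAP section 10.2 names possible grounds for a major deviation, including "Not being compliant with the study medication dosing schedule". It says only that these may be considered, gives no cut-off and does not refer to section 12.1. Protocol section 5.5 says that doses are given in the clinic and recorded, and defines no compliance measure.

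**The concern.** A compliance figure should compare the doses given with the doses due. Dividing by 17 does that only for subjects who reach the Week 56 dosing visit. For anyone stopped earlier, injections that never fell due are counted as not received, and when the sponsor ends the study those injections are ones the protocol itself says must not be given.

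The SAP adapted other elements to the termination: the interim analysis, sample size and multiplicity sections were all dropped or simplified. This definition was left as it would be for a study run to completion. Because 17 is a constant, the percentage also only rescales the injection count already reported as exposure. A reader of the clinical study report who looks to the compliance table for dosing adherence would be misled about subjects whose treatment was truncated.

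**Working it through.** **Reproducing the 17.** Dosing visits fall every 4 weeks from Week 0 to Week 56: 56/4 + 1 = 15 visits. One extra injection at each of Weeks 0 and 4 gives 15 + 2 = 17, which matches the SAP and the protocol.

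**A subject with no missed dose.** For a last dose at Week w (w = 4 or later), injections due = w/4 + 1 + 2. At Week 0 the number due is 2. The SAP score is that number divided by 17. The score against injections due is 100% in every row.

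| Last dose | Injections due and given | SAP compliance | SAP band |
|---|---|---|---|
| Week 0 | 2 | 2/17 = 11.8% | below 20% |
| Week 4 | 4 | 4/17 = 23.5% | 20 to below 40% |
| Week 12 | 6 | 6/17 = 35.3% | 20 to below 40% |
| Week 24 | 9 | 9/17 = 52.9% | 40 to below 60% |
| Week 36 | 12 | 12/17 = 70.6% | 60 to below 80% |
| Week 52 | 16 | 16/17 = 94.1% | 80 to below 100% |
| Week 56 | 17 | 17/17 = 100% | 100% |

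**Two different subjects, one score.** Subject A is stopped after the Week 24 dose with 9 of 9 due injections given: SAP score 9/17 = 52.9%, against 9/9 = 100% of doses due. Subject B is dosed through Week 56 but misses 8: SAP score (17 - 8)/17 = 52.9%, which is also 52.9% of doses due.

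**How many could be affected (illustration only).** The documents give neither a termination date nor last-dose dates. The rationale recorded for Amendment 7, dated 25 April 2016, speaks of the study as already terminated. Assume that dosing had stopped by then.

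- Fifty-six weeks before 25 April 2016 is 30 March 2015. Only 5 subjects had been randomised by 2 April 2015 (Amendment 5), so at most 5 of the 35 recorded at Amendment 7 could have reached the Week 56 dose.
- The 21 - 5 = 16 subjects randomised between Amendments 5 and 6 had at most 16 injections due.
- The 35 - 21 = 14 randomised after 28 September 2015 (Amendment 6) had at most 30 weeks on study, so at most 10 injections due and a ceiling of 10/17 = 58.8%.

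These counts cannot be taken further. SAP sections 1 and 5 report 69 subjects randomised, while Amendments 7 and 8 both report 35.

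**The case against.** The best defence is that the ratio sits under the heading Extent of Exposure, where injections received over 17 is a correctly calculated share of the planned course. The injection count is also summarised and listed, and SAP section 10.1 tabulates completion and reasons for withdrawal by arm, so a reader can recover the distinction from other outputs. The table is descriptive and feeds no test. This stands as a limit on importance. It does not rescue the label, because the SAP calls the ratio compliance and nothing in section 12.1 warns that early stopping lowers it.

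Three stronger readings are tempting but not supported.

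- A reader might infer that adherent subjects are classed as non-compliant. Section 12.1 sets no threshold and applies no such label; it reports a percentage and a band.
- A reader might infer that sponsor-stopped subjects would leave the per-protocol set and push it below the 50% of ITT at which that analysis is dropped. That needs the section 10.2 criterion to be adopted, to use the section 12.1 percentage and to have a cut-off that catches truncated subjects. The SAP states none of these. A subject stopped because the sponsor ended the study has followed the protocol.
- A reader might infer that the bands merely restate time on study. Missed, held or skipped doses lower the score too.

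Changing the denominator also has a drawback. Someone who chooses to stop after Week 0 would score 2/2 = 100%. The course fraction must therefore be kept beside it.

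**Conclusion.** The definition is wrong as written for any subject whose dosing ended before Week 56, and no other part of either document corrects it. For a subject with no missed dose, the understatement runs from 6 percentage points (last dose Week 52) to 88 points (last dose Week 0). Subjects dosed through Week 56 are scored correctly.

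The consequence is a descriptive table that cannot separate truncation from missed doses. Exposure is reported correctly and no efficacy result uses the percentage directly. An effect on the per-protocol set is conditional on a decision that the SAP leaves open.

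The point rests on the SAP's statement of early termination and on the protocol's rule that termination ends study drug. It does not depend on the illustrative counts above. If some subjects continued dosing to Week 56 after termination, fewer are affected, but the definition remains wrong for the rest.

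**What to change.** In SAP section 12.1:

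- Define compliance as injections received divided by injections scheduled up to the subject's discontinuation or termination date, which is 17 for anyone who reaches the Week 56 dosing visit.
- State whether a dose skipped under the dose-holding rule in Protocol section 4.4.1 stays in the denominator.
- Report injections received over 17 separately, labelled as the percentage of the planned course, so that early stoppers who score 100% on compliance remain visible.
- If a per-protocol criterion on dosing compliance is adopted under section 10.2, base it only on the corrected figure.

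This needs a few sentences in the SAP and a small programming change. The new inputs are the subject's stop date and the dosing schedule, so no further data collection should be needed.

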12.2. Adverse Events

AEs will be collected from the start of study treatment (treatment emergent AEs) through the follow-up contact.

SAEs will be collected over the same time period as stated above for AEs. However, any SAEs assessed as related to study participation (e.g., study treatment, protocol-mandated procedures, invasive tests, or change in existing therapy) or related to a concomitant medication, will be recorded from the time a subject consents to participate in the study up to and including any follow up contact.

AEs will be categorized by their occurrence in regard to therapeutic period (pre-therapy, on-therapy, follow-up or individualized follow-up) as defined in Section 9.3.2. Any events that occur prior to initiation of investigational product will be reported as medical history. If, however, a prior event is reported on the AE page of the eCRF it will be reported as 'pre-therapy' AE. Pre-therapy AEs will be presented only in data listings and will not be summarized.

All AEs will be coded using Medical Dictionary for Regulatory Activities (MedDRA) and summarized based on system organ class (SOC) and PT. Summaries by treatment group of the number and percentage of subjects with an AE will be presented in alphabetical order by SOC. Within the SOC level, the PTs will be presented in descending order of incidences. A PT will not be presented if no AEs occur within the level.

An overview summary of the number and percentage of subjects with any AE and the total number of AEs recorded during the randomized treatment period will be presented by treatment group. For the AEs recorded in the follow-up (FU) period if there are not enough events to summarize (i.e. <10 events) then the data of those AEs will be listed only otherwise it will be summarized. If any AEs recorded in the individualized follow-up period it will be listed only.

For AE listings, AE duration will be defined as (the date of resolution of the AE – the onset date of the AE) + 1 day. If no date of resolution is provided, AE duration will be presented as 'Continuing'.

12.2.1. Counting Rules for AEs

In the summary tables, the following rules apply when counting AEs:

1. If a subject experiences the same AE (i.e. same PT) more than once during a study period, they are only counted once under the count for the PT.
2. If a subject experiences more than one AE (i.e. differing PTs) in a particular SOC, they will only be included once in the count for the SOC, but will appear in the count for each appropriate PT within the SOC (unless it is the same PT, see Point 1. above). As a result, the sum of the numbers of subjects with each event (i.e. PT) within a SOC may exceed the number of subjects with events within that SOC. Similarly, the sum of the SOC totals may exceed the total number of subjects with at least one event.

12.2.2. Overall Adverse Events

Summaries of the number and percentage of subjects with TEAEs and the total number of TEAEs will be provided by treatment group at the SOC and PT level for on-therapy period. For the AEs recorded in the follow-up (FU) period if there are not enough events to summarize then the data of those AEs will be listed only otherwise it will be summarized for the follow-up period. If any AEs recorded in the individualized follow-up period it will be listed only.

A by-subject listing of all AEs will also be presented.

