8.3.6.9. Safety Analyses

The analysis of safety data will use the Safety population. These data will not undergo any formal statistical analysis.

Adverse Events

Adverse events will be coded using the MedDRA and summarized by system organ class and preferred term.

Summaries by treatment groups, of the number and percentage of subjects with the following AEs will be provided:

- All AEs
- Adverse event frequency, severity, and relationship to investigational product
- Frequency and severity of infections
- Frequency of SAEs
- Percentage of subjects withdrawing due to AEs assessed by the investigators as at least possibly related to treatment
- Adverse events leading to permanent discontinuation of investigational product
- Adverse events of special interest (see Section 6.3.2.3)
- Postinjection systemic reactions
- Injection site reactions

The hierarchical relationship between MedDRA, system organ classes, and preferred terms and verbatim text will be displayed for relevant AEs.

Clinical Laboratory Evaluations

Summary statistics will be presented for each laboratory test, and change from baseline, at each assessment time point by treatment group. Laboratory test values will be flagged to show whether they are a value within, below, or above the normal range and if they are a value of potential clinical concern. The number and percentage of subjects with values in each of these categories at each assessment time point will be summarized for each laboratory test.

Vital Signs

Each variable and change from baseline in each variable will be summarized at each assessment time point by treatment group. In addition, the number and percentage of subjects with vital sign values within, below, and above values of potential clinical concern will be summarized for each variable.

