12.3. Deaths and Serious Adverse Events

All SAEs will be summarized in a manner similar to that described above for the overall AE summary by treatment group. By-subject listings of all non-fatal SAEs and all deaths will be presented.

12.4. Adverse Events Leading to Discontinuation of Investigational Product and/or Withdrawal from the Study and Other Significant Adverse Events Incidents

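### Adverse events are shown only as crude percentages and counts although time at risk varies between subjects, so the tables do not describe a full treatment course and could mislead between arms if stopping differs by arm

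*SAP*

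**What the plan says.** SAP 12.2.2 sets the main AE table: "Summaries of the number and percentage of subjects with TEAEs and the total number of TEAEs will be provided by treatment group". SAP 12.2 adds an overview of the same kind: "An overview summary of the number and percentage of subjects with any AE and the total number of AEs recorded during the randomized treatment period". SAEs follow suit in SAP 12.3: "All SAEs will be summarized in a manner similar to that described above for the overall AE summary by treatment group". Protocol 8.3.6.9 also plans summaries "of the number and percentage of subjects with the following AEs will be provided".

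Exposure in SAP 12.1 is "the number of injections each subject received", and "Percentage subject compliance will be defined as the number of injections received/17 planned injections". Neither document plans a duration of exposure, patient-time, an exposure-adjusted rate or a time-to-first-AE analysis.

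SAP 9.3.2 defines the on-therapy period as running from the first dose to 4 weeks after the last dose. SAP 4.2 says: "The study was terminated early and the final analysis will be conducted on the available data". SAP 1 and 5 give 69 randomized subjects. Protocol 4.4.2 makes sponsor termination a mandatory reason to stop investigational product. The same list includes "Subject initiates treatment with a prohibited PV disease-modifying drug". SAP 12 states that safety data get no inferential analysis.

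**The concern.** A crude percentage has a clear meaning when everyone is observed for the same period. Here each subject's window closes 4 weeks after that subject's own last dose, and termination cut dosing short at different points for subjects who entered at different times. Two things are at stake.

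First, the percentages understate what would be seen over a completed course. This needs no imbalance between arms.

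Second, the side-by-side comparison mixes event rate with length of observation. If one arm stops sooner, for example because more of its subjects start a prohibited pemphigus drug, it accrues fewer events for that reason alone. Protocol 8.3.6.1 recognizes this problem for time to sustained remission: it discusses shortened exposure through unequal discontinuation and adds a sensitivity analysis. Safety has no counterpart, and without patient-time by arm a reader cannot adjust the AE tables directly.

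**Working it through.** **1. The plan's own exposure figure.** Dosing visits at Weeks 0, 4, ..., 56 number 15. One extra injection at Weeks 0 and 4 gives 15 + 2 = 17, as SAP 12.1 states. With no dose missed, the on-therapy window is 4 weeks per dosing visit: 4 visits (6 injections) give 16 weeks, 8 visits (10 injections) give 32 weeks, and 15 visits (17 injections) give 60 weeks. A subject stopped after 8 fully dosed visits therefore shows 10/17 = 58.8% compliance without having missed a dose.

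**2. Does time at risk vary?** The amendment history in Protocol Appendix 15 gives the numbers randomized: 5 at 2 April 2015, 21 at 28 September 2015 and 35 at 25 April 2016. The last of these amendments already describes the study as terminated. From 2 April 2015 to 25 April 2016 is 389 days = 55.6 weeks, so at least 35 − 5 = 30 of those 35 had entered less than 56 weeks earlier. From 28 September 2015 is 210 days = 30 weeks, so 35 − 21 = 14 had entered at most 30 weeks earlier. The documents do not give actual stop dates, and the SAP total is 69. These counts show staggered entry, not final exposure.

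**3. Effect on the absolute percentages.** Assume a constant hazard λ, so that risk over t weeks is 1 − exp(−λt). The 60-week risks are assumptions, since the documents give no AE rates.

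| Risk over 60 weeks | At 48 weeks | At 36 weeks |
|---|---|---|
| 10% | 8.1% | 6.1% |
| 30% | 24.8% | 19.3% |
| 60% | 52.0% | 42.3% |

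**4. Effect between arms when the true hazards are equal.** Crude incidence = 1 − exp(−h × weeks/52), with h first events per patient-year. Both h and the mean times at risk are assumed.

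| h | 48 weeks | 44 weeks | Gap (points) | 36 weeks | Gap v 48 weeks (points) |
|---|---|---|---|---|---|
| 0.5 | 37.0% | 34.5% | 2.5 | 29.3% | 7.7 |
| 1 | 60.3% | 57.1% | 3.2 | 50.0% | 10.3 |
| 2 | 84.2% | 81.6% | 2.6 | 75.0% | 9.3 |

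Expected total events scale with time: 48/44 = 1.09 and 48/36 = 1.33. At equal exposure every gap is zero. If ofatumumab is the shorter arm, the signs reverse. The model gives every subject the arm mean, which is a simplification.

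**5. Which denominator removes the gap?** Dividing subjects with a first event by *total* on-therapy time does not. At 48 v 36 weeks with equal hazards:

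- h = 0.5: 0.370/(48/52) v 0.293/(36/52) = 40.0 v 42.3 per 100 patient-years
- h = 1: 65.3 v 72.2
- h = 2: 91.2 v 108.3

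The longer-exposed arm now looks safer. If person-time stops at the first event, its expected value per subject is [1 − exp(−hT)]/h, where T is the window in years. The ratio of expected events to expected person-time is then h in both arms, whatever T is.

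**The case against.** A reader might infer that the planned tables are biased against ofatumumab. The documents do not support that. They give no exposure by arm. Termination acts on both arms of a 1:1 randomization, so in expectation it shortens both about equally. It creates variation between subjects, not between arms. The arm-linked route is also narrow: a flare is not itself a stopping reason, because Protocol 3.1.2 handles it by changing the prednisone dose. Only starting a prohibited drug ends dosing, and no rate is given for that. All of this stands.

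The 12-week gap is large against the one attrition figure available. Protocol 8.2.1 assumes at most 13% lost to follow-up. If 13% of one arm left on Day 1 and nobody left the other, the mean gap would be 0.13 × 60 = 7.8 weeks. That figure predates termination and is not the same as stopping drug, but it makes 48 v 44 weeks the more moderate case. With 34 and 35 per arm and incidence near 55%, the standard error of a difference is √[0.55 × 0.45 × (1/34 + 1/35)] = 0.12, or about 12 points, so even 10.3 points is below one standard error.

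Injection count does track duration under fixed 4-weekly dosing, and SAP 12.1 and 10.1 show injections, compliance bands and withdrawal reasons by arm. A marked imbalance would be visible. This answers the point only in part: injections are never used as an AE denominator, and Protocol 4.4.1 allows held doses to be skipped, so count and time can diverge.

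Finally, the SAP openly declares a reduced plan, and no safety test is affected. That lowers the priority. It does not supply the missing information, because side-by-side description is the only safety comparison planned.

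**Conclusion.** The point holds in a limited form. Time at risk varies between subjects, and the planned crude percentages and totals do not account for it. As descriptions of a 56-week course they are therefore incomplete, whatever the balance between arms. Between-arm distortion is possible but conditional on differential stopping. Its direction is not known, and it is zero at equal exposure. Under constant and equal hazards of 0.5 to 2 per patient-year, a 4-week difference in mean time at risk gives about 2.5 to 3.2 points, and a 12-week difference gives 7.7 to 10.3. Both differences are assumed. Type I error, power and sample size are untouched. The priority lies between optional and recommended.

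**What to change.** In SAP 12.1, add duration of on-therapy exposure and patient-years by arm, counted from first dose to last dose + 28 days and cut at data cut-off or end of follow-up if earlier.

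In SAP 12.2.2 and 12.3, beside n (%), add the exposure-adjusted incidence rate per 100 patient-years with 95% CI for any AE, SAEs and the Infections system organ class. Define it as subjects with a first event divided by patient-time from first dose to that first event, or to the end of the on-therapy window if there is none. If total events are shown as a rate, divide them by total on-therapy patient-years instead.

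The cost is a few columns, since the on-therapy classification already needs first-dose, last-dose and AE onset dates. The drawback is that these rates assume a roughly constant hazard, which is doubtful for events that cluster around the first injections. They should supplement the crude percentages, not replace them.
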